7.3.5. Pharmacogenomic Endpoints

In this present study, we propose to examine potential genetic determinants of treatment response and particular adverse events by studying the patient's genomic profile in relation to treatment outcome and presence or absence of the adverse events. A single blood sample will be obtained at an unscheduled post-study visit, with invited participants first providing separate written, signed informed consent for pharmacogenomic analysis. The final list of pharmacogenomic endpoints will be delineated in the SAP for the pharmacogenomic portion of the study.

7.4. Efforts to Minimize Missing Data

It is important to avoid missing data from clinical trials. The following strategies are designed to minimize drop-outs and missing data in this study:

- Providing patients with greater background on the nature of placebo-controlled clinical trials and explaining that completing this study, regardless of the patient's level of treatment response, is essential to understanding whether TNX-102 SL may be helpful to others in the treatment of PTSD. Sites will explain that the study is not designed to benefit the individual patient but, rather, can only provide useful information for future therapeutics.
- Minimizing the burden on patients, with visits scheduled generally every 4 weeks (with reasonable visit window flexibility). Clinical site personnel will also receive guidance regarding the special considerations necessary when dealing with patients with military PTSD.
- Training of site personnel on the importance of minimizing missing data
- Providing payment for patients' time and effort at clinic visits, based on the duration of assessments and as approved by the Institutional Review Board. Reimbursement for travel expenses to and from the clinic sites may also be provided to further minimize the financial burden of participating in the study.
- Utilizing repeated assessments of outcome measures and analytical approaches that most appropriately compensate for missing data.

8. SELECTION AND WITHDRAWAL OF PATIENTS

8.1. Informed Consent

A potential patient may be screened for eligibility only after the nature of the study, its purpose, and any other information relevant to the patient's decision to participate have been explained to him or her and the patient has voluntarily confirmed his or her willingness to participate. If medications are to be withdrawn for the explicit purpose of participation in this study, the patient must first sign an informed consent form before the withdrawal or down titration of any medication is initiated.

Informed consent is documented by means of a written, signed, and dated informed consent form (ICF). Separate written, signed informed consent must be obtained if the patient is to participate

in the post-study pharmacogenomic assessment. Additional information is provided in [Section 15.3](#).

8.2. Inclusion Criteria

Patients enrolled in this study will be volunteer patients. Eligible patients must meet all of the following inclusion criteria during the screening period:

1. Male or female between 18 and 75 years of age, inclusive, with military service (defined as active duty military, National Guard, reservist, veteran or military contractor) Identification confirming military service will be checked prior to randomization; medical monitor approval will be required for potential patients unable to provide evidence of prior service.
2. Diagnosed with current PTSD as determined by the Clinician-Administered PTSD Scale (CAPS-5) for Diagnostic and Statistical Manual of Mental Disorders-Version 5 (DSM-5) and of sufficient symptom severity, defined as all of the following at Screening Visit 1 using the Diagnostic version (1-month recall):
 - a. The A criterion is 1=YES, and
 - b. At least ONE item of the B criterion items must have a score of ≥ 2 , and
 - c. At least ONE item of the C criterion items must have a score of ≥ 2 , and
 - d. At least TWO items of the D criterion items must have a score of ≥ 2 , and
 - e. At least TWO items of the E criterion items must have a score of ≥ 2 , and
 - f. The F item 22 criterion is 1=YES (≥ 1 month duration of symptoms)
 - g. At least ONE item of the G items must have a score of ≥ 2 , and
 - h. The total CAPS-5 score (of items 1 through 20 is) ≥ 33 .
3. Index trauma(s) resulting in PTSD must meet the following:
 - a. DSM-5 criterion A for PTSD as described in the CAPS-5 and Criterion A – Assessment Form (CA-AF), and
 - b. Must have occurred in 2001 or later, and
 - c. Must be military service related (either occurrence during military service, including during National Guard service or as reservist), and
 - d. Must have occurred when the patient was ≥ 18 years of age.
4. Willing and able to withdraw and refrain from opioids for the course of the study.
5. Willing to refrain from use of all other formulations of cyclobenzaprine for the course of the study.
6. Willing and able to refrain from antidepressants, antipsychotics, mood stabilizers, anticonvulsants, benzodiazepines, non-benzodiazepine hypnotics, buspirone, stimulants (e.g. amphetamines, methylphenidate, modafinil, armodafinil), prazosin and trazodone for the course of the study.
7. Capable of reading and understanding English and able to provide written informed consent to participate.
8. If female, either not of childbearing potential (defined as postmenopausal for at least one year or surgically sterile [e.g., bilateral tubal ligation; bilateral oophorectomy;

hysterectomy, etc.]) or practicing one of the following medically acceptable methods of birth control throughout the study:

- a. Hormonal methods such as oral, implantable, injectable, or transdermal contraceptives for a minimum of one full cycle (based on the patient's usual menstrual cycle period) before study drug administration;
 - b. Intrauterine device (IUD);
 - c. Double-barrier method (condoms, sponge, diaphragm, or vaginal ring with spermicidal jellies or cream);
 - d. In sexually-exclusive relationship with vasectomized male partner, or in same-sex relationship with no plans for artificial or other forms of insemination.
9. Willing and able to comply with all protocol-specified requirements.
10. If patient has received trauma-focused treatment (e.g., cognitive behavioral therapy for PTSD, prolonged exposure therapy, desensitization therapy, etc.) must have been completed at least three months prior to the Baseline visit, and there can be no plans to initiate this type of therapy during study. General psychotherapy that was in process at time of Screening may be continued during the trial, but no new initiation of treatment is allowed during the trial after enrollment.
11. Separate written, signed informed consent will be required if the patient is to participate in the post-study pharmacogenomic assessment. To be eligible to participate in the Pharmacogenomic assessment, the patient must have been randomized, had at least one post-baseline CAPS-5 assessment, and received active study drug in the TNX-CY-P301 study.

8.3. Exclusion Criteria

Eligible patients who meet any of the following criteria during the screening period should be excluded from the study:

1. Increased risk of suicide on the basis of the investigator's judgment and/or the results of the Mini International Neuropsychiatric Interview, Version 7.0.2 (M.I.N.I. 7.0.2) conducted at Screening and the Columbia Suicide Severity Rating Scale (C-SSRS) conducted at Screening and/or Baseline. Any of the following will be exclusionary:
 - a. High suicidality based on a M.I.N.I. Module B score ≥ 17 (Screening); or,
 - b. Patient answers YES to either M.I.N.I. question B10 or B11 (Screening); or,
 - c. Patient meets criteria for CURRENT Suicidal Behavior Disorder on the M.I.N.I (Screening); or,
 - d. C-SSRS Type 4 or Type 5 ideation within 6 months of Screening or at the Baseline visit; or,
 - e. Any suicidal behavior in the past 12 months as identified by the C-SSRS at Screening or Baseline.
2. Increased risk of suicide, based on the investigator's judgment that is of a severity that is not appropriate for outpatient management, or that warrants additional therapy excluded by the protocol.

3. Significant (e.g., moderate or severe) comorbid traumatic brain injury (TBI) by history. Based on past history and investigator's judgment, patients with mild TBI are eligible.
4. Evidence of severe depression at screening or baseline (Visits 1 or 2) based on the investigator's judgment and collaborative pre-randomization review by the investigator and medical monitor(s) of the patient's psychiatric history, presenting symptomatology, M.I.N.I. 7.0.2 (including Major Depressive Episode and Suicidality modules), C-SSRS, CAPS-5, and BDI-II assessments.
5. Clinically significant laboratory abnormalities based on screening laboratory tests and/or medical history in the investigator's opinion, including a Thyroid Stimulating Hormone (TSH) level >1.5 times the upper limit of normal and aspartate aminotransferase (AST) and/or alanine aminotransferase (ALT) > 3 times the upper limit of normal (if persistent upon repeat). Patients with treated thyroid conditions and TSH levels ≤ 1.5 times the upper limit of normal will be eligible to participate in the study.
6. Diagnosed with clinically significant cardiac disease (e.g., significant arrhythmia or heart block, heart failure, or recent myocardial infarction [within the past 2 years]) or QTcF >450 msec (male) or >470 msec (female) on the screening electrocardiogram (ECG).
7. Current evidence of human immunodeficiency virus (HIV) infection based on screening laboratory results or medical history, or clinically significant hepatitis B or C infection as defined by current treatment or liver function tests (e.g., aspartate aminotransferase [AST] or alanine aminotransferase [ALT] > 3 times the upper limits of normal).
8. Use of antidepressant medication within 2 months of baseline, with the exception of trazodone used at doses ≤ 150 mg per day or tricyclic antidepressants at doses ≤ 25 mg per day, which instead require a 1-week drug-free interval prior to the Baseline visit.
9. Unable to successfully wash out of the following medications during screening, or in whom washout is medically inadvisable: anticonvulsants, mood stabilizers, anti-psychotic agents, opioids, benzodiazepines, non-benzodiazepine hypnotics (zolpidem; eszopiclone, zaleplon), buspirone, trazodone, stimulants (e.g., amphetamine mixed salts, methylphenidate, lisdexamphetamine, dextroamphetamine, modafanil, armodafanil), atomoxetine, or any medication known to be a potent (strong) cytochrome P450 subtype 3A4 (CYP3A4) inhibitor, or St. John's wort. **Note:** Use of caffeine and/or nicotine is permitted.
10. Unable to successfully wash out of alpha-adrenergic antagonists and/or agonists (e.g., prazosin, terazosin, doxazosin, tamsulosin, silodosin, tizanidine, clonidine, guanfacine) or when washout is medically inadvisable.
11. Positive results for illegal or abused substances other than cannabis at Screening or Baseline or history of alcohol/substance use disorder during the preceding 6 months as defined by the screening M.I.N.I. 7.0.2. Patients who utilize alcohol/cannabis but do not meet criteria for alcohol/substance use disorder are otherwise suitable for the study provided that, in the judgment of the Investigator, this usage will not interfere with the patient's ability to complete the study or provide reliable data.
12. Any clinically significant, uncontrolled, or unstable medical or surgical condition that could affect a patient's ability to participate in the study or potentially compromise a

patient's well-being during the study, including patients with a history of untreated or uncontrolled angle-closure glaucoma.

13. Diagnosis of DSM-5-defined bipolar disorder I, II or unspecified, schizophrenia, schizoaffective disorder, obsessive-compulsive disorder, major depressive disorder (MDD) with psychotic features, other psychotic disorder, or antisocial personality disorder as confirmed by the M.I.N.I. Version 7.0.2.
14. History within the past 2 years of violent behavior unrelated to military duties or associated work.
15. Anticipated need for surgery that might confound results or interfere with patient's ability to comply with the protocol.
16. Female patients who are pregnant or lactating.
17. History of serotonin syndrome, severe allergic reaction or bronchospasm or known hypersensitivity to cyclobenzaprine or the excipients in TNX-102 SL or placebo formulations.
18. Seizure disorder other than history of childhood febrile seizures.
19. Current sleep apnea not well controlled by Continuous Positive Airway Pressure (CPAP) or oral (mouthpiece) devices. Patients with mild obstructive sleep apnea or those well controlled by CPAP or oral (mouthpiece) devices are allowed at the discretion of the investigator.
20. Patients with a body mass index (BMI) > 45.
21. Has received any other investigational drug within 30 days before Screening or has taken cyclobenzaprine within 21 days before Randomization visit.
22. Previous participation in any other study with TNX-102 SL.
23. Any existing oral medical or dental condition, or tongue piercings, that could potentially interfere with sublingual administration of study drug, or history of severe or unexplained oral or oropharyngeal swelling or edema.
24. Family member of investigative staff.
25. In the process of litigating for compensation for a psychiatric disorder. Patients who are in the process of applying for VA benefits or who have a settled claim are eligible.

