 - e. Any suicidal behavior in the past 12 months as identified by the C-SSRS at Screening or Baseline.
2. Increased risk of suicide, based on the investigator's judgment that is of a severity that is not appropriate for outpatient management, or that warrants additional therapy excluded by the protocol.
3. Significant (e.g., moderate or severe) comorbid traumatic brain injury (TBI) by history. Based on past history and investigator's judgment, patients with mild TBI are eligible.
4. Evidence of severe depression at screening or baseline (Visits 1 or 2) based on the investigator's judgment and collaborative pre-randomization review by the investigator and medical monitor(s) of the patient's psychiatric history, presenting symptomatology, M.I.N.I.

- 7.0.2 (including Major Depressive Episode and Suicidality modules), C-SSRS, CAPS-5, and BDI-II assessments.
5. Clinically significant laboratory abnormalities based on screening laboratory tests and/or medical history in the investigator's opinion, including a Thyroid Stimulating Hormone (TSH) level >1.5 times the upper limit of normal and aspartate aminotransferase (AST) and/or alanine aminotransferase (ALT) > 3 times the upper limit of normal (if persistent upon repeat). Patients with treated thyroid conditions and TSH levels ≤ 1.5 times the upper limit of normal will be eligible to participate in the study.
 6. Diagnosed with clinically significant cardiac disease (e.g., significant arrhythmia or heart block, heart failure, or recent myocardial infarction [within the past 2 years]) or QTcF >450 msec (male) or >470 msec (female) on the screening electrocardiogram (ECG).
 7. Current evidence of human immunodeficiency virus (HIV) infection based on screening laboratory results or medical history, or clinically significant hepatitis B or C infection as defined by current treatment or liver function tests (e.g., aspartate aminotransferase [AST] or alanine aminotransferase [ALT] > 3 times the upper limits of normal).
 8. Use of antidepressant medication within 2 months of baseline, with the exception of trazodone at doses ≤ 150 mg per day or tricyclic antidepressants at doses ≤ 25 mg per day, which instead require a 1-week drug-free interval prior to the Baseline visit.

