8.4. Randomization Criteria

The following randomization criteria must be satisfied at the Visit 2 Baseline Randomization Visit in order for the patient to be eligible to continue in the study. Only those patients meeting all of the following randomization criteria are eligible for randomization:

1. Patient continues to meet all inclusion and exclusion criteria, including urine and blood test results, and
2. Visit 2 total CAPS-5 score ≥ 33 ("Symptom Severity version using 1-week recall), and

3. At Visit 2, patient is not severely depressed (based on the investigator's judgment and Visit 2 C-SSRS, CAPS-5, and BDI-II, and considering the pre-randomization collaborative review by the investigator and medical monitor(s) of the patient's Visit 1 psychiatric history, presenting symptomatology, M.I.N.I. 7.0.2, C-SSRS, CAPS-5, and BDI-II assessments).
4. No active suicidal intent or plan, based on Investigator's judgment, and Visit 2 C-SSRS responses (e.g., no C-SSRS Type 4-5 ideation or suicidal behavior since Visit 1).

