10.1.4. Screening and Assessments/Procedures

The following screening assessments/procedures will be completed in the following general order:

- Obtain written informed consent to participate

- Obtain demographics, including alcohol, nicotine/tobacco (smoking and/or chewing), and marijuana use
- Obtain medical history
- Obtain prior and current medication history, including all prior PTSD therapies and other treatments for psychiatric indications
- Obtain psychiatric history (M.I.N.I. 7.0.2)
- Administer PTSD Rating Scales:
 - Life Events Checklist (LEC-5)
 - Criterion A – Assessment Form (CA-AF)
 - Clinician Administered PTSD Scale (CAPS-5) (Since Last Month version)
- Perform physical examination, including visual inspection of the oral cavity (including floor of mouth/sublingual area)
- Obtain vital signs, height, weight and BMI
- Draw samples for clinical laboratory tests for:
 - Chemistry, hematology, HIV and TSH, with free thyroxine also performed if TSH is outside the upper or lower limits of normal
 - Urine Drug Screen (central laboratory)
 - Serum pregnancy test (for women of child-bearing potential)
- Conduct 12-lead electrocardiogram
- Administer Depression/Suicidality Scales
 - Beck Depression Inventory (BDI-II)
 - Columbia Suicide Severity Rating Scale (C-SSRS, Baseline/Screening Version, with rater review of BDI-II prior to starting C-SSRS interview)
- Review inclusion/exclusion criteria

Only those patients meeting all of the inclusion and none of the exclusion criteria will be eligible to continue. NOTE: Final determination of eligibility based on clinical laboratory tests will be made when results have been returned.

Sites will be asked to complete and submit to the Tonix medical monitoring team key screening information. This information will be reviewed by the Tonix medical monitoring team to help ensure the selection of well-qualified patients. The specific requirements and timelines associated with this pre-randomization review process will be outlined in a separate document.

Once eligibility has been confirmed and authorization for randomization granted by a Tonix medical monitor, eligible patients will return to the clinic for Visit 2.

There is no requirement for Follow-Up visits for patients who are screen failures. Patients who fail to qualify should have their medication adjusted, as appropriate, per the judgment of the

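### Hyperthyroidism, a contraindication in the appended cyclobenzaprine label, is not a named exclusion, and the treated-thyroid sentence in criterion 5 has no low-TSH or free thyroxine condition

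*Protocol*

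**What the plan says.** Exclusion criterion 5 (Protocol section 8.3) has three parts.

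- A general clause, left to the investigator's opinion, that excludes for "Clinically significant laboratory abnormalities based on screening laboratory tests and/or medical history".
- Named examples of such abnormalities. The thyroid example is TSH above 1.5 times the upper limit of normal.
- A closing sentence on treated disease: "Patients with treated thyroid conditions and TSH levels ≤ 1.5 times the upper limit of normal will be eligible". The synopsis carries the same sentence.

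Table 2, footnote c, restates the high-side TSH limit. The repeat-test rule in section 11.3.8 covers only values that stay elevated. Section 10.1.4 has TSH drawn at screening "with free thyroxine also performed if TSH is outside the upper or lower limits of normal", but no section attaches an exclusion level to the free thyroxine result.

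Other provisions that bear on the same patient:

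- Criterion 12 excludes for "Any clinically significant, uncontrolled, or unstable medical or surgical condition" that could affect participation or well-being.
- Section 10.1.4: "Only those patients meeting all of the inclusion and none of the exclusion criteria will be eligible to continue". It also requires "authorization for randomization granted by a Tonix medical monitor" before Visit 2.
- Randomization criterion 1 (section 8.4): "Patient continues to meet all inclusion and exclusion criteria, including urine and blood test results".

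Appendix 3 reproduces the label for an oral extended-release cyclobenzaprine capsule. It lists hyperthyroidism as a contraindication in the highlights and in label section 4, and its patient information tells people with an overactive thyroid not to take the drug.

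**The concern.** The label's contraindication has no counterpart among the named exclusions, and the one sentence written specifically for treated thyroid disease points toward eligibility. It guards against under-treatment (high TSH) but is silent on over-treatment or active hyperthyroidism (low TSH with raised free thyroxine), which is the side the label warns about.

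A site holding such a result has to weigh a general judgement clause against a specific sentence that reads as permission. Sites could reasonably differ. At stake is the exposure of a hyperthyroid patient to a drug whose active ingredient is contraindicated for that condition in a label the protocol itself attaches. The estimate of treatment effect is not at stake.

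**Working it through.** No formula applies and the plan states no figure to reproduce. The check is a reading of the eligibility text against the label.

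**Step 1: named exclusions.** Criteria 1 to 25 in section 8.3 were read for hyperthyroidism, a low TSH limit or a free thyroxine limit. Result: 0 of 25. The randomization criteria (section 8.4) and the medication rules (section 8.5) add none.

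**Step 2: numeric thyroid limits.** There is one distinct limit, TSH above 1.5 times the upper limit of normal, in criterion 5. Table 2 footnote c repeats it, and the repeat rule in section 11.3.8 addresses elevated values only. There are no low-side limits.

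**Step 3: the four contraindications in label section 4, set against the protocol.**

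| Label contraindication | Where the protocol addresses it by name |
|---|---|
| Hypersensitivity | Criterion 17 |
| MAO inhibitors | Section 15.3 |
| Recent infarction, arrhythmia, conduction disease, heart failure | Criterion 6, largely |
| Hyperthyroidism | Nowhere |

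Three of the four are addressed by name. The fourth is not.

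**Step 4: apply the written rule to a treated patient with TSH below normal and free thyroxine above normal.**

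- Numeric TSH exclusion: not met, because a low TSH is below 1.5 times the upper limit.
- Treated-thyroid sentence: satisfied as worded.
- General clause of criterion 5: can exclude, if the investigator considers the abnormality clinically significant.
- Criterion 12: can exclude, if the condition is judged clinically significant, uncontrolled or unstable.
- Medical monitor: can withhold authorization. The protocol states no thyroid rule for that review.
- Section 10.1.4 and randomization criterion 1: enforce the exclusions above, but add no thyroid test of their own.

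Every route to exclusion therefore turns on judgement.

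**Step 5: compare with other permissive sentences on clinical conditions.** Mild brain injury (criterion 3), alcohol or cannabis use (criterion 11) and controlled sleep apnea (criterion 19) are each allowed subject to the investigator's judgement or discretion. Stable hepatitis (section 7.1) needs prior medical monitor approval. The thyroid sentence carries no such qualifier.

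**The case against.** The strongest reply is that the plan already handles the case. In criterion 5 the TSH and liver enzyme limits are introduced as examples, so the general clause reaches low TSH with raised free thyroxine. The closing sentence is most naturally read as the converse of the limit just before it: treated disease is no bar if TSH is not too high. It need not override the clause it belongs to. Reflex free thyroxine brings the result into view, and a medical monitor must agree before randomization. Most of this stands, and it is why an overt case would probably be excluded. It does not remove the tension with an unqualified sentence on exactly this group of patients.

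A second reply is that the label is not the trial's eligibility standard. It covers 15 and 30 mg oral capsules, whereas the study drug is 5.6 mg sublingual, and the protocol departs from other label advice by enrolling to age 75 and dosing for 12 weeks. This stands as a limit on weight. Those departures concern warnings and limits of use, however, whereas hyperthyroidism is a contraindication, listed beside three that the protocol does address.

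Third, the Investigator's Brochure and the separate pre-randomization review document are not available here and may contain a thyroid rule. That is fair, so the point concerns the protocol text only.

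Two stronger readings are tempting. One is that criterion 5 admits hyperthyroid patients. The documents do not support it, because the sentence does not switch off the other exclusions. The other is that the gap is larger because TSH and the 12-lead ECG are scheduled at Visit 1 only. That describes later monitoring and does not measure a gap in the entry rule. Vital signs including heart rate and weight, adverse event reporting and unscheduled visits also continue after entry.

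**Conclusion.** The point holds as a gap in the written eligibility rule. A labelled contraindication of the active ingredient has no named exclusion, and the sentence on treated thyroid disease literally covers a patient who is biochemically hyperthyroid. Exclusion rests on judgement clauses that would probably, but not certainly, work.

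Its size is small. The patients at risk of exposure are those among the 275 planned for the active arm (550/2) who have treated thyroid disease with low TSH and raised free thyroxine at screening. The documents give no frequency, so no count can be derived; the number is probably very small. An untreated hyperthyroid patient falls outside the treated-thyroid sentence, but is likewise excluded only by judgement. The efficacy analysis is unaffected.

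The conclusion assumes that the appended label is a reasonable safety reference for the active ingredient despite the difference in formulation and dose, and that no unseen document already settles the matter. It is an optional, cheap improvement.

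**What to change.** Edit four places.

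1. Criterion 5, in the synopsis and in section 8.3: add as an exclusion *current hyperthyroidism, including TSH below the lower limit of normal with free thyroxine above the upper limit of normal (if persistent upon repeat)*. The word *including* matters. The label says hyperthyroidism without a biochemical definition, and a rule that defined it only by this laboratory pattern would be narrower.
2. The closing sentence of criterion 5, in the same two places: end it with *provided they are not currently hyperthyroid*.
3. Table 2, footnote c: add the same exclusion.
4. The repeat rule in section 11.3.8: refer to values that *remain exclusionary* on repeat, in place of values that stay elevated, so that it also works on the low side.

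A treated patient with low TSH and normal free thyroxine is not caught by the laboratory example and stays subject to the existing judgement clauses. No new first-line test is needed, since TSH and reflex free thyroxine are already run at screening. The cost is an occasional repeat test and a few extra screen failures.
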